Study Product, Dose, Route, Regimen	
Criteria for successful iFI are locations of all EGFR positive samples (defined as having a pathology score ≥ 1 based on histological staining) having a measurable signal (defined as SNR ≥ 10). A single microdose of ABY-029 at 30 nanomoles (237μg) will be injected into the first 3 patients. If samples from these subjects meet successful iFI criteria, 3 more patients will be enrolled at the same dose, concluding the study with a total of 6 subjects. Otherwise, the ABY-029 dose in the next 3 patients will be increased to 3X (90 nanomoles, 711 μg). If samples from these subjects meet successful iFI criteria, 3 more patients will be enrolled at the 3X dose, concluding the study with a total of 9 subjects. If iFI criteria are not met, the next 3 patients will be enrolled at 6X dose (180 nanomoles, 1.42 mg). If iFI criteria are met, 3 more patients will be enrolled the 6X dose, concluding the study with a total of 12 subjects. If iFI criteria are not met in the first 3 patients at the 6X dose, enrollment will be stopped with a total of 9 subjects.
 
Because of the microdosing levels used, the results of the Dartmouth Toxicity Study (at 10X, 100X, 1000X doses), and the safety profile of similar compounds (e.g. ABY-025), we do not anticipate any serious adverse events (SAEs) related to ABY-029.

Duration of administration	ABY-029 will be administered by IV injection on day of surgery, approximately 1-3 hours prior to the procedure.
Reference methods	Post-operative histopathology will serve as the gold standard.
Statistical Considerations	Repeated measures analyses of variance will be performed to account for multiple samples from each patient. Student's t-test will be used to evaluate ABY-029 fluorescence signal detection in tumor relative to normal brain with iFI and intraoperative probe. Empirical ROC curves and logistic regression analysis for clustered binary data will be used to evaluate the accuracy of ABY-029-specific fluorescence in discriminating between EGFR+ glioma tumor, EGFR- glioma tissue, and normal tissue when detected by iFI and/or intraoperative probe.

1 Introduction

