1.3.2 Toxicology study (GLP)

The preclinical toxicology assessment is based on a single-dose toxicity study in one species conducted at Dartmouth.

• Extended single-dose Safety Study in rats

We conducted a definitive, extended single-dose toxicity study of ABY-029 in Sprague-Dawley rats, consistent with the principles outlined in "Guidance for Industry, Investigators, and Reviewers: Exploratory IND Studies" (2006). This study used the non-GMP-manufactured ABY-029 batch created at UAB, which was also used to develop the GMP process.

A maximum microdose is 30 nmol per 60 kg human subject (or ~237 µg for a protein drug, or 3.95 µg/kg in a human), and this study used the equivalent rat dose of 4.898 µg for a 0.20 kg rat (allowing for a 6.2X rat-to-human correction for skin surface area). Following review of FDA guidelines and pre-IND meetings with FDA, doses of 10X, 100X and 1000X were studied to evaluate whether pharmacologically relevant effects exist. The dose levels tested were 0.049 mg, 0.49 mg and 4.9 mg in the rat toxicity study, along with a control group.

Total Study Duration	1 day and 14 day post-injections
Recovery	Control and high dose group, sacrifice and analysis on day 15
Route	IV (bolus)
Frequency of dose	single
No of doses	1
Groups	Control and 3 dose groups
No of animals	6 male + 6 female per group
Dose levels (preliminary)	0 µg/kg 244.9 µg/kg 2449 µg/kg 24490 µg/kg

Main study	Day 0 - ABY-029 administration
Recovery period	1 or 14 days
Analysis	All standard parameters: Clinical signs, post-dosing observations, standard ophthalmology, body weight, haematology, bone marrow smears, clinical chemistry, macroscopic examination and organ weights, histopathology

A comprehensive set of protocol tissues was collected during necropsy and sent to a veterinary pathologist for microscopic examination. No histopathologic evidence of systemic toxicity was associated with the single-dose (10X, 100X, 1000X) intravenous administration of ABY-029 after 24 hours or 14 days in the study rats. Further, no toxic effects were observed among any of the animals during the routine daily checks.

- Biodistribution Study in normal rats**

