1.4 Clinical Data to Date

While no clinical data is available to date on the experimental investigational product, the component molecules Z03115-Cys and IRDye800CW have been used in clinical trials, and products similar to ABY-029 have gone to clinical trial as well.

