1.4.1 Related Affibody product ABY-025

ABY-025 (Z_{HER2:2891}-Cys-MMA-DOTA), is a HER2-specific Affibody® molecule that targets a radionuclide to HER2-receptor expressing tumors, for in vivo diagnosis of HER2-expressing cancer. ABY-025 is a 61 amino acid peptide that is modified site-specifically with one DOTA molecule at the side chain of the C-terminal cysteine. DOTA acts as chelator for the radionuclide Indium-111 (¹¹¹In) or Gallium-68 (⁶⁸Ga). An Investigational Medicinal Product Dossier (IMPD) for ABY-025 labeling with ⁶⁸Ga or ¹¹¹In has been filed for clinical studies in Sweden and Denmark, as outlined below.

- 1) ABY-025-MI103 (EudraCT 2010-021078-12, NCT01216033)

An exploratory study to evaluate the distribution of [¹¹¹In]ABY-025 uptake for SPECT imaging in subjects with metastatic breast cancer. This study included 7 patients and was completed in Sweden in 2011, with results published [39]

- 2) ABY-025-MI105 (EudraCT 2012-005228-14, NCT01858116).
An exploratory study to evaluate [⁶⁸Ga]ABY-025 for PET imaging of HER2 expression in subjects with metastatic breast cancer was due to have been completed in December 2014. This study was initiated 2013 in Swede68n and 16 patients were enrolled to receive at least 2 doses of ABY-025. No adverse events with possible or probable relationships to the study drug were reported, and seven non-serious adverse events with “unlikely” relationships to the study drug were noted [40].
- 3) MA 1021 (EudraCT 2010-024353-36, NCT02095210)
An exploratory study of HER2 PET imaging in breast cancer patients using [⁶⁸Ga]ABY-025 was completed. This study was conducted in Denmark from October 2010 to April 2013 with 8 patients enrolled. Results have been published [41]

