1.5 Dose Rationale

We plan a sample size of 6-12 patients in this open label, single center, clinical trial of ABY-029. Administration will occur as a single intravenous injection to subjects with recurrent glioma, approximately 1-3 hours prior to surgery. The protocol is not a safety study since no physiological effects are expected at microdose levels of ABY-029. Rather, doses have been selected to determine if a fluorescence signal can be detected by wide-field imaging technology with a signal-to-noise ratio of 10, which is considered necessary for subsequent assessment of diagnostic performance of ABY-029 as a tumor biomarker sufficient to guide surgical resection in the future. No diagnostic or therapeutic intent is proposed, and administration of the study drug is not intended to alter the extent of planned brain tumor resection during the surgical procedure.

Dosing Scheme: A single microdose of ABY-029 at 30 nanomoles (237 μ g) will be injected into the first 3 patients. If samples from these subjects meet successful iFI criteria (defined as SNR \geq 10 at locations of samples with EGFR pathology score \geq 1 based on histological staining), 3 more patients will be enrolled at the same dose, concluding the study with a total of 6 subjects. Otherwise, the ABY-029 dose in the next 3 patients will be increased to 3X (90 nanomoles, 711 μ g). If samples from these subjects meet successful iFI criteria, 3 more patients will be enrolled at the 3X dose, concluding the study with a total of 9 subjects. If iFI criteria are not met, the next 3 patients will be enrolled at 6X dose (180 nanomoles, 1.42 mg). If iFI criteria are met, 3 more patients will be enrolled at the 6X dose, concluding the study with a total of 12 subjects. If iFI criteria are not met in the first 3 patients at the 6X dose, enrollment will be stopped with a total of 9 subjects.

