1.6.1 Potential Risks

Because of the microdose levels to be used, the results of the Dartmouth Toxicity Study, and the safety profile of similar compounds (e.g. ABY-025), serious adverse events (SAEs) related to ABY-029 are not expected to occur.

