3.1 General Design

This study is a Phase 0 open label, single-center clinical trial of ABY-029, an Anti-EGFR Fluorescence Imaging Agent, via single intravenous injection to subjects with recurrent glioma. The expected duration for enrolling study participants is 12 to 18 months, and up to 12 subjects may be enrolled. Doses of 1X (30 nanomoles or 237 μ g), 3X, and 6X may be considered depending on strength of signal detection with iFI in tissues within the surgical field, subsequently sampled and determined post-operatively to have positive EGFR scores based on histological staining.

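### The dosing scheme steps up to 3X and 6X on imaging failure alone; a one-sentence hold for a drug-related serious or unexpected event should be added

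*Combined protocol and SAP*

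**What the plan says.** Three patients receive 1X. If the imaging criterion (SNR of at least 10 at the sites of EGFR-positive samples) is not met, the synopsis and section 1.5 both direct: "Otherwise, the ABY-029 dose in the next 3 patients will be increased to 3X". After a second failure: "If iFI criteria are not met, the next 3 patients will be enrolled at 6X dose (180 nanomoles, 1.42 mg"). The only stopping rule in the scheme is also an imaging failure, at 6X. Section 3.1 is softer, saying that the doses "may be considered depending on strength of signal detection with iFI in tissues within the surgical field", but it too names only signal strength.

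On the dose ceiling, section 1.3.2 says: "A maximum microdose is 30 nmol per 60 kg human subject". Section 1.4 records that "no clinical data is available to date on the experimental investigational product".

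Section 1.6.1 gives three grounds for expecting no drug-related serious events: "Because of the microdose levels to be used, the results of the Dartmouth Toxicity Study, and the safety profile of similar compounds". The rat study in 1.3.2 reports: "No histopathologic evidence of systemic toxicity was associated with the single-dose (10X, 100X, 1000X) intravenous administration of ABY-029". For one trial of the related compound ABY-025, section 1.4.1 states: "No adverse events with possible or probable relationships to the study drug were reported".

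Section 8 has the team log and review every adverse event. Unexpected and/or serious events go to the DSMAC, although a later sentence narrows reporting to outcomes not routinely expected in these surgical patients. Summaries go for review yearly, or more often depending on enrollment. Unexpected or serious events judged likely related to study procedures go to the IRB and FDA. Section 6 describes about 30 days of surveillance through routine care.

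**The concern.** A dose-escalation rule should say what happens if the drug appears to have caused harm at the current level. This one answers only the imaging question. Followed literally, the dosing paragraph moves to the next dose on imaging failure whether or not a related serious event has been seen.

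Section 1.5 explains that this is not a safety study because no physiological effect is expected at microdose levels. By the definition in 1.3.2, that reason covers 1X but not, by itself, 3X or 6X. At stake is the protection of the patients who would receive the higher doses, if such an event occurred at a lower one.

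**Working it through.** **Doses against the stated ceiling.** Inputs: molecular weight 7914.95 g/mol (1.2); doses in 1.5; vial of 5 mL at 0.27 mg/mL (5.7), used whole for the 6X group (5.9.3).

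- Reproducing the plan's figures as nmol × molecular weight: 30 nmol = 237.4 µg, 90 nmol = 712.3 µg and 180 nmol = 1424.7 µg. These match the stated 237 µg, 711 µg and 1.42 mg to rounding.
- 3X as ordered: 711 µg / 7914.95 = 89.8 nmol, or 3.0 times 30 nmol.
- Nominal 6X as given: 5 × 0.27 = 1.35 mg; 1.35 / 0.237 = 5.70X; 1.35 mg / 7914.95 = 170.6 nmol.
- The ceiling is per 60 kg while trial doses are fixed. This does not rescue the higher doses: 90 nmol meets 30 nmol per 60 kg only at 90 / 30 × 60 = 180 kg.

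**Patients dosed above 30 nmol, by path of the scheme.**

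| Path | 1X | 3X | 6X | Above 30 nmol |
|---|---|---|---|---|
| 1X succeeds | 6 | 0 | 0 | 0 of 6 |
| 1X fails, 3X succeeds | 3 | 6 | 0 | 6 of 9 |
| 1X and 3X fail, 6X succeeds | 3 | 3 | 6 | 9 of 12 |
| All three fail | 3 | 3 | 3 | 6 of 9 |

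**Toxicology margin.** Rat doses were 244.9, 2449 and 24490 µg/kg, with a 6.2-fold rat-to-human correction (1.3.2).

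- Human equivalents: 39.5, 395 and 3950 µg/kg.
- Top human dose at 60 kg: 1350 / 60 = 22.5 µg/kg.
- Margins: 39.5 / 22.5 = 1.8 at the lowest rat dose and 3950 / 22.5 = 175.6 (about 175) at the highest.

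**What three patients can show.** The chance of at least one event is 1 − (1 − p)³. With assumed true rates of 5%, 10%, 20% and 30% it is 14%, 27%, 49% and 66%. No events in 3 patients leaves a one-sided 95% upper bound of 1 − 0.05^(1/3) = 63%. A clean cohort is therefore weak reassurance, whereas an observed related event is informative. That favors a hold triggered by an event over a routine safety stage.

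**Is the missing condition supplied elsewhere?** Section 3.1 names only signal. Section 8 says who is told about events and when summaries are reviewed, but not what happens to the next dose. Section 6 does not require surveillance to finish before the next group opens. Section 10.1 cites a cancer-center monitoring plan that is not in the documents and to which the dosing scheme does not refer.

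**The case against.** The strongest reply is that the omission is a reasoned choice and that oversight exists. The rat doses were set after meetings with FDA, and even the lowest exceeds the highest human dose after scaling. Section 6.2 adds that chemistry differences at 24 hours stayed within the normal range. Section 1.4 says both components of ABY-029 have been used in trials, and section 1.2 describes a 12-patient escalation study of the same dye on an antibody to the same receptor, reported as safe. Patients are under nurse observation from injection to surgery (5.4), with vital signs followed for at least 24 hours afterwards (6.2). All of this stands. It makes harm unlikely but does not say what to do if a related event occurs.

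A reader might infer three stronger things, none of which the documents support.

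- *That the trial lacks safety monitoring.* Section 8 refutes this. The broader of its two reporting sentences covers all serious events, expected or not.
- *That the trial would in practice escalate past a related serious event.* The DSMAC, IRB or FDA could intervene, and the unseen monitoring plan may allow a pause. The documents show only that no hold is written into the scheme.
- *That each step needs a completed 30-day window and committee sign-off on every surgical event.* Section 1.3.2 gives a rat plasma half-life of 15–20 minutes, no detectable plasma level at 48 hours and rodent tissue signal up to 72 hours, so no pharmacological reason for 30 days is evident. Two such waits would total up to 60 days, which is 60 / 548 = 11% to 60 / 365 = 16% of the 12–18 month duration. Patients whose surgery cannot wait might also be lost.

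**Conclusion.** The point holds in a limited form. The scheme makes both dose steps conditional on imaging failure only; both higher doses exceed the protocol's own ceiling (3.0 and 5.7 times); and no section provided ties an adverse event to the next dose. Severity is minor: expected harm is low, and nothing is affected if 1X succeeds. On any escalation path, 6 to 9 patients are exposed above 30 nmol.

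The margin of about 175 rests on the protocol's 6.2-fold correction and a 60 kg patient. The event rates used for three patients are assumptions. The conclusion about the missing link is limited to the documents at hand, since the monitoring plan could not be read.

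**What to change.** In the synopsis and 1.5, state that the next dose opens only if (i) the imaging criterion was evaluated and not met at the current dose, and (ii) no serious or unexpected adverse event judged likely related to ABY-029 has been logged in any patient dosed so far. If one has, escalation is held until the DSMAC has reviewed it and recorded that the next dose may open. Cross-refer to this in section 8, and have relatedness to ABY-029 judged explicitly, because that section now speaks of study procedures.

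A fixed 30-day wait and DSMAC sign-off on expected surgical events are optional and not part of this recommendation.

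This is a cheap improvement. It takes a sentence or two in each of three places and uses an existing committee and existing reports, with no added patients, visits or tests. The downside is a short delay, and only if such an event occurs; the documents do not give the committee's review time.

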1.6 Potential Risks and Benefits

The risks to subjects are reasonable in relation to anticipated benefits and/or knowledge that might reasonably be expected from the results of this clinical trial.

1.6.1 Potential Risks

Because of the microdose levels to be used, the results of the Dartmouth Toxicity Study, and the safety profile of similar compounds (e.g. ABY-025), serious adverse events (SAEs) related to ABY-029 are not expected to occur.

1.6.2 Potential Benefits

Patients enrolling in this study will not benefit directly because no diagnostic or therapeutic decisions will occur based on the study drug, and thus, administration of the study drug is not intended to alter the extent of planned brain tumor resection during the surgical procedure. However, future patients may benefit from the knowledge gained from the study. Current literature shows that maximum cytoreductive surgery is of significant benefit to patients with malignant gliomas. Patients with complete resections also experience survival benefits from post-operative radiation and/or chemotherapy. Unfortunately, achieving a high degree of tumor removal is often limited by the surgeon's ability to distinguish residual disease from intervening parenchyma under conventional white light illumination, and rates of complete resection have

been reported to be as low as 20% in high grade glioma. iFI augments the surgeon's white light visual field with fluorescent information, and in the case of ALA-induced PpIX, improved patient outcomes in a prospective randomized Phase III trial sufficiently to alter standard-of-care in Germany for surgical resection of high grade glioma. While ALA appears to be effective, motivation exists for pursuing new fluorescent probes beyond PpIX for guiding surgical resection. First, ALA-induced PpIX fluorescence is not tumor-specific. Second, fluorescent enhancement at the margin and in low-grade glioma is relatively poor. Third, ABY-029 has potential to guide a range of oncologic surgeries, given the large number of tumor types that overexpress EGFR. Fourth, a wealth of information exists on EGFR fluorophore targeting which suggests our approach is likely to be successful and could benefit patients with malignant glioma and other cancers whose prognosis is improved by complete surgical resection.

2 Study Objectives

The primary study objective is to determine if microdoses of ABY-029 (up to 6X) lead to detectable signals (defined as signal-to-noise ratio, SNR ≥ 10 , with wide-field iFI) in sampled tissues with an EGFR pathology score ≥ 1 based on histological staining.

The secondary study objectives are to assess the diagnostic accuracy of ABY-029 detection by iFI and an intraoperative probe relative to histopathology as the gold standard, and to measure the molecular uptake and concentration of ABY-029 in resected specimens.

3 Study Design

3.1 General Design

This study is a Phase 0 open label, single-center clinical trial of ABY-029, an Anti-EGFR Fluorescence Imaging Agent, via single intravenous injection to subjects with recurrent glioma. The expected duration for enrolling study participants is 12 to 18 months, and up to 12 subjects may be enrolled. Doses of 1X (30 nanomoles or 237 μ g), 3X, and 6X may be considered depending on strength of signal detection with iFI in tissues within the surgical field, subsequently sampled and determined post-operatively to have positive EGFR scores based on histological staining.

3.2 Primary Study Endpoints

The primary study endpoint is signal detection (defined as SNR with wide-field iFI) in vivo in brain tissues within the surgical field intended for resection that are subsequently sampled during surgery and assigned an EGFR pathology score based on histological staining.

3.3 Secondary Study Endpoints

Secondary endpoints of the study are diagnostic accuracy of ABY-029 detection by iFI and intraoperative probe relative to histopathology tissue diagnosis, and other indicators (e.g. proliferation, infiltration, etc.) as the gold standard, and measurement of molecular uptake and concentration of ABY-029 in resected specimens.

4 Subject Selection and Withdrawal

4.1 Patient Selection

Patients with recurrence of presumed high grade glioma having EGFR positive tissue (score ≥ 1 based on histological staining or molecular pathology analysis) obtained from prior surgery will be eligible to participate.

4.2 Inclusion Criteria

The following criteria must be met by study subjects to be eligible for study enrollment:

- 1) Preoperative diagnosis of recurrent high-grade glioma having EGFR positive tissue from prior surgery.

- 2) Tumor judged to be suitable for open cranial resection based on preoperative imaging studies.
- 3) Valid informed consent by subject.
- 4) Age \geq 18 years old.

4.3 Exclusion Criteria

The following criteria would exclude a subject from study enrollment:

- 1) Pregnant women or women who are breast feeding.
- 2) Patients on any experimental anti-EGFR targeted therapies

4.4 Subject Recruitment and Retention

Participation in this research requires informed consent according to Institutional Review Board (IRB) guidelines and a signed IRB-approved Consent Form as the means of documenting this understanding. Potential recruits are instructed that their participation is completely voluntary and that their medical care will not be altered in any way should they elect not to participate at any time prior to surgery. Subjects are recruited from patients presenting or referred to the Section of Neurosurgery at Dartmouth-Hitchcock Medical Center for surgical resection of intracranial tumor of the types meeting protocol inclusion criteria. Potential subjects may learn about the study through its posting on clinicaltrials.gov and contact [name] or another surgeon in the Neurosurgery Section about participation. Subjects will be invited to participate in this study by a member of the Neurosurgery Section which will occur either at the time of consultation with the surgeon about the candidate's standard-of-care procedures or at another time agreed to by the potential participant, the candidate's surgeon and/or [name] or [name] designee. No advertisements or other promotional material will be used. No finder fees or recruitment incentives will be offered. Women of child bearing potential are eligible for enrollment into this study because ABY-029 administration is not considered to present any additional risk for these women. The study will exclude women who are pregnant or breast-feeding as indicated in the exclusion criteria. Women of child-bearing potential, if asked to participate, will be given a pregnancy test at no cost to confirm pregnancy status before administration of ABY-029.

